During surgery, current clinical practice is to measure epileptic activity that we call epileptic spikes (on intra-operative ECoG) or seizure onset zone (extra-operative ECoG) with EEG recordings. Current clinical standard of practice in either intra-operative ECoG or extra-operative ECoG is recorded to identify epileptic zone and seizure onset zone. The presence of epileptiform brain activity/spikes, or the seizure onset zone, identified by clinical neurophysiologists, is used to guide the neurosurgeon with respect to the boundaries of brain tissue that is necessary for resection to achieve seizure freedom. The particular part of the brain that has either of these abnormalities, is removed. We have used this method for over 40 years.

New Research HFO Method

Recently, it has been discovered that we can also measure other epileptic activity, High Frequency Oscillations or HFOs, by recording EEGs at a higher frequency rate. These HFOs on the EEG recordings appear to point out the epileptic brain tissue better than epileptic spikes or seizure onset zone.

In this study we will compare the two groups of patients to see what works best: standard clinical practice only, or standard clinical practice along with HFOs. The results of this study may change the way we operate on epilepsy surgery patients in the future.

Hypothesis: We hypothesize that the strategy of incorporating HFO data to a standard ECoG-guided resection in pediatric epilepsy surgery will result in improved postoperative seizure outcome than the traditional approach.

Objective:

The primary objective is to determine if HFO data in addition to ECoG data (experimental group, arm 1), compared to standard ECoG data alone (current standard control group, arm 2), will lead to improved post-surgical seizure outcome 1 year after surgery.

Secondary objectives include the comparison of incidence of neurologic deficits, neuropsychological outcomes (when available with clinical testing), and quality of life outcomes.

Study Design and Procedures:

A single-blinded randomized control trial including subjects with refractory focal epilepsy who undergo surgery with intra- or extra-operative electrocorticography. Surgery is

tailored by HFOs and standard ECoG interpretation (spikes on intra-operative ECoG or seizure onset on extra-operative ECoG) (arm 1), or tailored by standard ECoG alone (arm 2).

Randomization

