Informed consent will be obtained 1 to 7 days to up to 3 months prior to the day of surgery. Prior to surgery, the subject will be randomized into the cohort arm in a 1:1 ratio.

Blinding

Blinding of the clinical neurophysiologists and neurosurgeons for treatment allocation is not feasible because of the character of the intervention. Therefore, this is a single-blinded trial as subjects will be blinded to the cohort arm to minimize bias of the follow-up results. The treating neurologist, if other than the clinical neurophysiologists in this study, will remain blinded.

Number of Subjects:

30

Inclusion Criteria:

- Age 0-21
- Refractory focal epilepsy
- Planned resective epilepsy neurosurgery with ECoG, with the goal of tailoring the resection

Exclusion Criteria:

- Subjects undergoing non-resective neurosurgery

Recruitment of Subjects:

Subjects with refractory epilepsy undergoing epilepsy surgery with ECoG to guide the extent of the resection.

Length of Study Visits and detail:

This research study will not require any additional time in the hospital after surgery. However, will be following the subject for epilepsy outcome up to 12 months after surgery.

Chart review of clinical records such as neurological, MRI, EEG and other clinically relevant information pertaining to the outcome of surgery will be collected.

Subjects or their caregivers will be asked to fill out questionnaires about seizure frequency, medication and day to day function in various life areas at each visit with the neurosurgeon/neurologist.

Schedule of events below:

PRE-SURGERY	SURGERY	POST-SURGERY				
		Visit 2	Visit 3	Visit 4	Visit 5	Visit 6
0 day-3 months prior to surgery		1-7 days after surgery	3 months	6 months	9 months	12 months

Pre-Surgery

- Consent
- Neurosurgeon visit
- Baseline Questionnaire

Post-Surgery (at every visit)

- Neurosurgery/Neurology Visit
- Follow-up Questionnaires

Questionnaires will take about 30 minutes to complete. We may send the questionnaires home a week prior to a return visit to alleviate time at the doctor's office.

Questionnaires

NIH Pediatric Stroke Scale

Child Behavior Check List

Quality of Life in Epilepsy (Adults)

Quality of Life in Childhood Epilepsy

Procedure Detail:

Intra-operative ECoG, which could be pre-resection, post-resection, or both, during brain surgery would be determined based on clinical decisions. Similarly, extra-operative ECoG would also be determined based on clinical decisions, and would be pre-resection.

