
For those subjects randomized to the standard clinical care with ECoG only (control arm), ECoG would be recorded but not assessed for HFO until after the clinical decision has been made with respect to site and margin of the resection. Only cortical areas deemed abnormal by standard clinical ECoG would be resected.

For those subjects randomized to the HFO + standard clinical care with ECoG combined (experimental arm), ECoG would be recorded AND assessed for HFO rapidly in the operating room (within 10 minutes) to minimize patient risk and while the neurosurgeon begins the initial resection. Should HFO persist after resection, further resection to ensure complete removal of HFO and standard clinical ECoG abnormalities may be possible. Cortical areas generating HFO and/or abnormal by standard clinical ECoG would be resected, with the exception of HFO-only presence in eloquent cortex, which would be spared. Eloquent cortex is defined as sensorimotor cortex, primary language cortex (Wernicke's and Broca's areas), and primary visual cortex.

Benefits of Study:

HFO analysis could determine/predict a better surgical outcome.

Potential Risks:

In epilepsy surgery there are always risks.

1. The patient may not become seizure free.
2. The patient may lose or may damage an area that is close to important function such as motor or speech functions.
3. The patient may develop a surgical complication such as infection, hydrocephalus or stroke.

In Standard Surgery plus HFO Method Risk: Additional risk may be unexpected neurologic deficit.

There will be every effort made to minimize loss of major brain function, such as language, motor skills, sensation, and vision, to what may be already anticipated from the standard clinical care approach. Should any of these 4 major brain function areas be found to have HFOs only, and not on standard ECoG analysis, these important areas of brain function will not be resected.

The likelihood of longer anesthesia time is very low since HFO analysis will begin before or concurrently with standard method. Therefore we do not expect any additional time under anesthesia for either method.

There is no additional risk of recording HFOs at higher frequencies. Higher frequency simply allows us to capture brain signals at higher frequency rate.

Randomization: There is no risk or benefit from randomization given that standard of care ECoG will be completed during surgery.

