**NCT03790280**

### **Statistical Analysis Plan (SAP):**

Our primary comparisons will be the comparison of post-surgery seizure free-time between the SOC and SOC+HFO study arms. The primary analysis will be a log-rank test. The secondary analysis of the primary endpoint will be a Cox-proportional hazards regression with seizure-free survival time as the outcome. Covariates will be treatment, and subject-level characteristics (ex. age and gender). Secondary outcomes of 2-year seizure-free rate will be assessed with logistic regression models using a similar set of covariates that will be included in the Cox model. Surgical complication rates will be compared using Fisher's exact tests for the overall analysis. The intent-to-treat principal will be utilized and subjects will be included in the randomized study arms for analysis rather than the actual treatment received. We will conduct a secondary analysis based on treatment received.

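### No by-arm review of harm is described during accrual, neurologic deficits have no specified analysis, and the one safety test the SAP names is too insensitive to support a statement about safety

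*SAP*

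**What the plan says.** **Intervention.** Under Procedure Detail, the control arm has resection only where standard ECoG is abnormal. In the experimental arm, "Cortical areas generating HFO and/or abnormal by standard clinical ECoG would be resected", except that eloquent cortex showing HFO alone is spared.

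**Named risk.** Potential Risks lists the general hazards of epilepsy surgery (continued seizures, functional loss, infection, hydrocephalus, stroke). For the HFO method it adds: "Additional risk may be unexpected neurologic deficit". No rate is given for any of these.

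**Planned harm comparisons.** The protocol's Objective section states: "Secondary objectives include the comparison of incidence of neurologic deficits". The SAP states: "Surgical complication rates will be compared using Fisher's exact tests for the overall analysis". It names no test or estimate for neurologic deficits, and no significance level, sidedness or timing for the Fisher's tests. The analysis is by randomised arm, with a secondary analysis by treatment received.

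**Data collected.** The visit schedule has post-surgery visits at 1-7 days and at 3, 6, 9 and 12 months. Follow-up questionnaires are completed at each, and the NIH Pediatric Stroke Scale is among those listed. Complications can be drawn from the planned chart review.

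**Oversight.** The text describes no interim tabulation of harm by arm, no monitoring body and no review of accumulating deficits. Blinding says that neurosurgeons and clinical neurophysiologists know the allocation, but nobody is assigned to compare the arms.

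**The concern.** Two separate weaknesses meet here.

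The first is timing. The intervention cannot be undone, the subjects are aged 0-21, and the protocol itself anticipates extra deficits in one arm. With no by-arm review described during accrual, all HFO-guided resections could be completed before any planned comparison of harm is made.

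The second is what the eventual comparison can show. The harm singled out for the HFO arm has no specified analysis. The harm that does have one is examined by a test with very little power at this sample size. If the report gave only a non-significant p-value, readers could not tell an absence of excess harm from an inability to see it.

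**Working it through.** **Inputs**
- Total sample size: "Number of Subjects: 30". The protocol gives no power, effect size or event rate with it, so there is no sample-size calculation to reproduce.
- Allocation: "the subject will be randomized into the cohort arm in a 1:1 ratio". This gives 30/2 = 15 per arm if balance is exact. No blocking is described, so 15/15 is an assumption.
- Test: "Fisher's exact tests for the overall analysis". Level and sidedness are not stated. I take two-sided 0.05 as the main case and show one-sided 0.05 as the alternative.
- True event rates: none in the documents. All rates below are assumptions.

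**Smallest result that reaches significance**

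With x events in the HFO arm, 0 in control and 15 per arm, the one-sided Fisher p-value is C(15,x)/C(30,x). With equal arms the distribution is symmetric, so the two-sided value is twice that.
- 4 v 0: 1,365/27,405 = 0.0498 one-sided, 0.0996 two-sided.
- 5 v 0: 3,003/142,506 = 0.0211 one-sided, 0.0421 two-sided.

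With one control event:
- 6 v 1: two-sided p = 0.080.
- 7 v 1: two-sided p = 0.035.

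| Control events (of 15) | HFO-arm events needed, two-sided 0.05 | One-sided 0.05 |
|---|---|---|
| 0 | 5 | 4 |
| 1 | 7 | 6 |
| 2 | 9 | 8 |
| 3 | 10 | 9 |

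The most favourable case at exact balance therefore needs 5/15 = 33% of the HFO arm harmed against none (4/15 = 27% at one-sided 0.05).

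Chance imbalance moves this slightly. Two-sided, 4/14 v 0/16 is enough (p = 0.0365), 5/16 v 0/14 is enough (p = 0.0447), and 5/17 v 0/13 is not (p = 0.0525).

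**Power**

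Power is the sum of Bin(x; 15, p1) × Bin(c; 15, p0) over all pairs (x, c) with x > c and Fisher p ≤ 0.05.

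| Assumed true risk, HFO v control | Two-sided 0.05 | One-sided 0.05 |
|---|---|---|
| 20% v 0% | 16.4% | 35.2% |
| 20% v 5% | 8.3% | 18.6% |
| 30% v 5% | 27.5% | 43.5% |
| 30% v 10% | 14.9% | 25.6% |
| 40% v 10% | 32.5% | 46.3% |

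**What zero events would show**

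The exact two-sided 95% upper limit for 0 of 15 is 1 − 0.025^(1/15) = 21.8%. Even an arm with no events is compatible with a true risk of about one in five.

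**Would repeating the test earlier help?**

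Hardly. At two-sided 0.05 with 8 or 10 per arm, 5 v 0 is still needed. With 4 or 5 per arm, 4 v 0 is needed. With 3 per arm the test cannot reach significance. An early review has to be a descriptive table, not an interim Fisher's test.

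**The case against.** Several points on the other side stand and limit the claim.

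- A reader might infer that Fisher's test is the only safety comparison in the trial. It is not. The Objective section also plans a comparison of neurologic deficits, and the SAP refers to tests in the plural. The supported statement is that Fisher's test on complications is the only safety test the SAP specifies.
- A reader might infer that the SAP fixes this test at the end of the study. It speaks of the overall analysis and gives no timing. What can be said is that no earlier look is described.
- A reader might infer that harm is compared late because the test has a high threshold. The two are independent. Lateness comes from the absence of a planned review, as the early-look calculation confirms.
- Safeguards exist. HFO-only eloquent cortex is spared, visits are frequent, and the operating team is unblinded and may notice deficits by arm. These lower the risk, but none is a planned comparison.
- Low power for harm is to be expected with 30 subjects in an unfunded study whose stated aim includes feasibility. The SAP nowhere says it will read non-significance as safety. That is a foreseeable misreading, not a stated plan.
- Oversight may exist outside the public documents. Absence is judged on the available text only.

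It is also tempting to demand a numerical pausing rule. The documents do not support choosing one. A rule that counted HFO-arm events alone could not separate HFO-related harm from ordinary surgical risk. To illustrate, a trigger at 2 or more of the first 5 or 3 or more of the first 10 would be reached with probability 2.8%, 11.3% or 38.9% if the rate in both arms were 5%, 10% or 20%. No document gives that rate.

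**Conclusion.** The concern holds in this form. The available text plans no by-arm review of harm during accrual for an irreversible intervention whose added risk the protocol names. The neurologic-deficit comparison has an objective but no analysis. The one specified safety test cannot on its own support a statement about safety.

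The size depends on assumptions the SAP leaves open. The threshold of 5 v 0 and the power of about 8% (20% v 5%) and 28% (30% v 5%) rest on 15 per arm, two-sided 0.05 and assumed event rates. At one-sided 0.05 the figures are 4 v 0, about 19% and 43.5%. The conclusion is the same under either reading. This is a change the trial should make. It does not show that the HFO strategy is unsafe, and it does not invalidate the primary comparison.

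**What to change.** **Protocol.** Add a by-arm tabulation of new neurologic deficits and of the complications listed under Potential Risks, at set points during accrual. One example is when the 5th and 10th HFO-arm subjects have early post-surgery visit data. Using an early visit matters because no accrual rate is given, and waiting for later visits could let most resections go ahead first. Send the table to the ethics board. Whether any count should hold randomisation, and which, is for the investigators and that board to decide.

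**SAP.**
- Analyse neurologic deficits as well as surgical complications by arm.
- Report each with exact 95% intervals for each arm and for the difference.
- State the level and sidedness of the Fisher's tests.
- State that a non-significant Fisher's test will not be taken as showing safety.

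**Cost.** Wording in both documents and two short tables from data already collected. A needless pause is possible if the board acts on a chance excess. Its probability depends on a background complication rate that the documents do not give. The tables should be kept from the subjects and from any treating neurologist who is blinded. They contain no efficacy data, so the log-rank test is unaffected.
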